12.7 Analysis of secondary efficacy endpoints

The following analyses will be performed as required (only listings may be presented depending on the study results).

12.7.1 ORR, DCR

The confidence intervals of ORR and DCR will be constructed using an exact method based on a binominal distribution. When subgroup analysis is performed, proportions or odds ratios will be compared among subgroups using appropriate analytical procedures, such as Fisher's exact test and logistic regression.

12.7.2 PFS, OS

By estimating survival functions using the Kaplan-Meier method, median survival times and their confidence intervals will be constructed, as well as annual survival rates and their confidence intervals. The confidence intervals for median survival times will be estimated by the Brookmeyer and Crowley method. The confidence intervals for annual survival rates will be estimated using Greenwood's formula. When subgroup analysis is performed, treatment responses compared among

the subgroups will be summarized using appropriate analytical procedures, such as the log-rank test and Cox proportional hazards model.

The survival time will be calculated by defining 1 year as 365.25 days and 1 month as 365.25/12 days. The calculation formula is [("Event date" or "Censoring date") – "Study enrollment date" + "1 day"].

12.8 Target sample size

[Dose escalation cohort] 3 to 6 patients at each level; 12 to 18 patients in total

[Expansion cohort] About 30 patients in total

12.9 Rationale for the sample size

See Section "6. Treatment Regimen and Treatment Modification Criteria."

12.10 Interim analysis

No interim analysis will be performed in this study.

12.11 Final analysis

All endpoints will be analyzed in the final analysis. The final analysis will be performed according

to the protocol and the analysis results will be reported in the clinical study report.

12.12 Special notes on analysis items

12.12.1 Items summarized and analyzed in the final analysis

In the final analysis, the following items will be analyzed.

<Items to be summarized>

- Demographic data
- Concomitant therapies
- Changes in laboratory values

To summarize a continuous variable, general descriptive statistics (mean, median, minimum, maximum, etc.) will be calculated.

<Items to be analyzed>

- Incidence of AEs
- Objective response rate (ORR)
- Disease control rate (DCR)
- Progression-free survival (PFS)
- Overall survival (OS)

<Subgroup analysis to be performed>

Subgroup analyses will be performed in an exploratory manner for the following factors. In these

analyses, adequate statistical power is not guaranteed and adjustment for multiplicity is not performed. Therefore, the results of each subgroup analysis will be interpreted as exploratory results.

- Cancer type
- Presence or absence of anti-PD-1 antibody use in the prior treatment

Since data on the following factors will be collected in an additional study to this study, the following subgroup analysis results will not be included in the clinical study report of this study.

- PD-L1 (Negative / Positive)
- MMR (Proficient / Deficient)
- TMB (High / Low)

etc.

12.12.2 Analysis items included in the clinical study report

The following analysis items will be included in the clinical study report.

<Efficacy evaluation (Analysis population: all enrolled patients)>

- Demographic data
- Objective response rate (ORR)
- Disease control rate (DCR)
- Progression-free survival (PFS)
- Overall survival (OS)

<Safety evaluation (Analysis population: SP)>

- Incidences of DLTs/AEs (number of patients with DLTs/AEs and the incidence, by the worst grade)
- Summary statistics of laboratory values and their changes

<Tables, figures and graphs referred to but not included in the text of the clinical study report>

- Listings of deaths, other serious and significant adverse events
- Laboratory value listing by patient

<Appendix>

- List of discontinued patients
- List of patients with serious protocol deviations
- List of patients excluded from FAS
- History of prior treatment
- List of concomitant medications and therapies
- Compliance
- List of efficacy response data by patient (tumor assessment, OS, PFS, subsequent treatment, and tumor markers)
- Adverse event listing by patient

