6.1.4 Target subjects for DLT evaluation

For each level, at least three subjects will be enrolled, and the presence or absence of DLT will be evaluated during the DLT evaluation period.

When it is determined that there is a subject who will not change levels, an additional subject will

be enrolled to evaluate the DLT determined in 6.1.3.

Furthermore, among the enrolled subjects, those who meet the following conditions will be excluded from DLT evaluation:

1) Subjects who are unable to receive regorafenib for ≥ 14 days in the first course for reasons other than toxicity.

2) Subjects for whom sufficient data cannot be obtained to determine the DLT evaluation because of missing mandatory tests, etc.

3) Cases in which adequate data for DLT evaluation judgment could not be obtained due to essential test defects

Furthermore, among the participants who withdraw from regorafenib and nivolumab during the first course for reasons other than adverse events or who withdraw from treatment for a long period because of toxicities other than DLT, the decision to subject such patients to a DLT evaluation will be determined upon deliberation between the trial coordinating committee and the participating institution.

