12.2 All enrolled patients

"All enrolled patients" are defined as patients enrolled in this study in accordance with Section "5.

Enrollment," excluding those who have been enrolled multiple times or mistakenly enrolled.

| 10 0 | D | • . • | e | | | |
|------|-------|-------|-------|---------|-------|---------|
| 12.5 | Defin | ition | of an | 9 VCIC | nonii | lations |
| 14.0 | Dum | nuon | or an | ary 515 | popu | autons |

Each analysis population is defined below.

| Abbreviation | Analysis population | Definition |
|--------------|---------------------|---|
| None | DLT analysis set | See Section "6. Treatment Regimen and |
| | | Treatment Modification Criteria." |
| SP | Safety population | The population of patients who received |
| | | the investigational product at least once |
| | | among all enrolled patients. |
| FAS | Full analysis set | The population of patients that excludes |
| | | those to whom the following applies |
| | | from all enrolled patients: |
| | | • Patients who should have been judged |
| | | as clearly ineligible based on the |
| | | information before enrollment |
| | | (ineligible patients). |

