12.6 Safety analysis

12.6.1 Analysis of the incidence of AEs

The occurrences of AEs in the SP will be summarized. Confidence intervals will not be constructed, and subgroup analysis will not be performed.

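### Section 12.12.2 reports DLT incidence on the Safety Population, while the DLT analysis set defined in 12.3 is used by no listed analysis

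*Combined protocol and SAP*

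**What the plan says.** Section 12.12.2 sets out what goes into the clinical study report. Its safety block is headed "<Safety evaluation (Analysis population: SP)>", and the first item under that heading is "Incidences of DLTs/AEs (number of patients with DLTs/AEs and the incidence, by the worst grade". DLTs and AEs share one bullet and one population.

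Section 12.3 defines three populations. One is the "DLT analysis set", defined only by reference to Section 6. Another is the SP: enrolled patients who received "the investigational product at least once". The SP is limited neither to the escalation cohort nor to patients evaluable for DLT.

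The other analysis sections do not assign DLTs to the DLT analysis set:

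- Section 12.5 treats dose-level decisions as monitoring and names no population.
- Section 12.6.1 concerns AEs only: "The occurrences of AEs in the SP will be summarized".
- Section 12.11 states "All endpoints will be analyzed in the final analysis" and names no population.
- Section 12.12.1 lists "Incidence of AEs" and has no DLT item.

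Section 6.1.4 says who counts for DLT. Among enrolled subjects, "those who meet the following conditions will be excluded from DLT evaluation".

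**The concern.** The plan creates a population for DLTs and then assigns the reported DLT incidence to a different one. DLT is the basis of the primary endpoint, the MTD and RD of regorafenib in the combination. A reader of the study report should be able to find in it the n/N that fixed the RD. On the SP, the denominator can include patients whom the protocol removed from DLT evaluation and, read literally, expansion patients for whom DLT was never part of the plan. Either one lowers the reported rate if no DLTs are counted in those patients.

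A table on the DLT analysis set added later would not cleanly repair this. Section 12.4.2 has analyses outside the planned final analysis flagged as not planned in advance, and the opening of Section 12 requires changes to the plan to be described in the report.

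**Working it through.** The plan gives no DLT rate to reproduce, so the check compares the two populations and then illustrates the effect on the rate.

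**Step 1: can the SP and the DLT analysis set differ?** Yes, in two ways.

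- *Within the escalation cohort.* Section 6.1.4 excludes, for example, patients who miss 14 or more days of regorafenib in course 1 for reasons other than toxicity, and patients with insufficient DLT data. It leaves some others to case-by-case deliberation. Such patients can have been dosed, and then they remain in the SP. Section 6.1.2 adds patients to the level when DLT cannot be properly evaluated, so treated patients can outnumber the 3 or 6 evaluable ones.
- *Between cohorts.* The SP includes about 30 expansion patients (12.8). Table 6.1.1a sets DLT numbers per escalation level, and 6.1.5 places the last DLT evaluation period before expansion. Section 12.12.2 does not ask for a split by cohort or dose level.

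**Step 2: table split by dose level.** Take d DLTs, 6 evaluable patients, and x treated but excluded patients with no DLT counted in them. The rate is d/6 on the DLT analysis set and d/(6 + x) on the SP. The values of d and x are assumed.

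| d | DLT analysis set | SP, x = 0 | SP, x = 1 | SP, x = 2 |
|---|---|---|---|---|
| 0 | 0/6 = 0% | 0/6 = 0% | 0/7 = 0% | 0/8 = 0% |
| 1 | 1/6 = 16.7% | 1/6 = 16.7% | 1/7 = 14.3% | 1/8 = 12.5% |
| 2 | 2/6 = 33.3% | 2/6 = 33.3% | 2/7 = 28.6% | 2/8 = 25.0% |

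The falls are 2.4 and 4.2 points for d = 1, and 4.8 and 8.3 points for d = 2.

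**Step 3: how often would x be at least 1?** The documents give no exclusion rate. With an assumed rate r per treated patient, independent between patients, the chance of at least one exclusion before n evaluable patients are reached is 1 − (1 − r)^n. The escalation cohort is planned at 9 to 18 patients (2.8.2; 12.8 gives 12 to 18).

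| r | One level, n = 6 | Whole escalation cohort, n = 9 to 18 |
|---|---|---|
| 2% | 11.4% | 16.6% to 30.5% |
| 5% | 26.5% | 37.0% to 60.3% |
| 10% | 46.9% | 61.3% to 85.0% |
| 20% | 73.8% | 86.6% to 98.2% |

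**Step 4: table with both cohorts pooled.** Assume at least one DLT in escalation, none counted in 30 expansion patients, and no exclusions. For N escalation patients the rate is divided by (N + 30)/N:

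- N = 9: 39/9 = 4.33
- N = 12: 42/12 = 3.50
- N = 15: 45/15 = 3.00
- N = 18: 48/18 = 2.67

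For example, two DLTs are 2/9 = 22.2% of 9 escalation patients but 2/39 = 5.1% of the pooled SP. At the RD dose alone, 1/6 = 16.7% becomes 1/36 = 2.8%.

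**The case against.** The strongest reply is that Section 6 already settles who counts. A patient excluded from DLT evaluation has no DLT status to tabulate, so the specific rule in 6.1.4, which 12.3 takes over by reference, should govern a general heading placed over a merged bullet. Section 12.4 also lets the coordinating committee settle population questions with the data center. On that reading this is loose wording and nothing more.

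That is a sensible guess at the intention, but the explicit assignment to the SP remains. Producing the table on the DLT analysis set would depart from the written plan, and 12.4 only provides a way to decide later.

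Four points on size do stand:

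- No dose decision, test or confidence interval depends on the figure.
- Pooling is an unlikely reading, because Sections 2.8 and 6 tie DLT evaluation to the escalation cohort. The multiples in Step 4 are a bound and should not drive the severity.
- The exclusion rates in Step 3 are assumptions. Section 12.12.2 asks for the number of patients with DLTs as well as the incidence, so the numerator stays visible.
- A level with two DLTs in six patients cannot be the RD under 6.1.2, so that row of Step 2 never describes the recommended dose. With no DLT at the RD level, the rate is 0% on either population.

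**Conclusion.** The concern holds. Section 12.12.2 assigns DLT incidence to the SP, and the population defined for DLTs is used nowhere in the listed analyses. This is a wrong stated rule and not a missing detail. Following it can give an n/N that differs from the one behind the MTD and RD.

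The effect is confined to reporting. The MTD and RD follow the per-level counts in 6.1.2 and are not touched. In a table split by level, the reported rate is unchanged if no treated patient is excluded. For one DLT in six evaluable patients it falls by 2.4 to 4.2 points with one or two exclusions. The 2.7- to 4.3-fold dilution arises only if the cohorts are pooled. These sizes rest on assumed DLT counts, assumed exclusions, and no DLT counted in excluded or expansion patients. The point should be fixed because it concerns how the primary-endpoint data are shown and the repair is cheap.

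**What to change.** In 12.12.2, split the combined bullet in two:

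- Incidence of DLTs: DLT analysis set, dose-escalation cohort, n/N by dose level.
- Incidence of AEs by worst grade: SP.

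Laboratory summaries stay on the SP. In 12.12.1, add incidence of DLTs (DLT analysis set) to the items to be analyzed, so that the table is part of the planned final analysis. It would also help if 12.3 pointed to 6.1.4 directly.

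Optionally, add an appendix list of treated escalation patients left out of the DLT analysis set, with reasons. The appendix already lists patients excluded from the FAS but has no equivalent for DLT evaluation.

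The cost is a few lines of text. It needs no new data and no change to trial conduct. The reported DLT rate will be the same as on the SP or higher if, as assumed above, no DLTs are counted outside the DLT analysis set.

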13 ETHICAL MATTERS

13.1 Policies, Laws and Regulations with Which the Study Complies

This clinical study will be conducted in compliance with the protocol, Declaration of Helsinki (http://www.med.or.jp/wma/), Article 80-2 of the PAL, "Ministerial Ordinance on Good Clinical Practice (GCP)" (Ordinance No. 28 of the Ministry of Health and Welfare dated March 27, 1997) and its revisions, and related notifications.

13.2 Informed Consent

13.2.1 Explanation to the Patients

- 1) That the study involves research
- 2) The purpose of the study
- 3) The name, title and contact address of the principal investigator or subinvestigators
- The method of the study (including the experimental aspect of the study and inclusion/exclusion criteria for the patients)
- 5) Expected clinical benefits and foreseeable risks or inconveniences
- 6) The availability of alternative therapies and their important potential benefits and risks
- 7) The expected duration of the patient's participation in the study.
- 8) That the patient's participation in the study is voluntary and that the patient may refuse to participate or withdraw from the study, at any time, without penalty or loss of benefits to which the patient is otherwise entitled.
- 9) That the monitor(s), the auditor(s), and the regulatory authority(ies) will be granted direct access to the patient's source documents without violating the confidentiality of the patient, and that, by signing the informed consent form, the patient is authorizing such access.
- 10) If the results of the study are published, the patient's identity will remain confidential.
- 11) The person(s) to contact for further information regarding the study and the rights of patients, and whom to contact in the event of study-related injury.
- 12) The compensation and/or treatment available to the patient in the event of study-related injury
- 13) The approximate number of patients involved in the study
- 14) That the patient will be informed in a timely manner if information becomes available that may be relevant to the patient's willingness to continue participation in the study

- 15) The foreseeable circumstances and/or reasons under which the patient's participation in the study may be terminated.
- 16) The anticipated expenses, if any, to the patient for participating in the study.
- 17) The anticipated payment, if any, to the patient for participating in the study.
- 18) The patient's responsibilities
- 19) Type of the IRB investigating and reviewing the appropriateness of the study, matters to be investigated and reviewed by each IRB, and other study-related matters concerning the IRB.
- 20) That the patient may check the written procedures for the IRB set forth in the preceding item and should request if he or she wants to do so. In addition, if the written procedures for the IRB, etc. are disclosed on a website, the fact that the address of the website is provided. If not disclosed, the fact that they are publicly available for review.
- 21) That data may be secondarily used.

13.2.2 Informed Consent

The investigator should request the patients to participate in the study after giving an explanation on the study and sufficient amount of time to think to the patients, and confirming that they have understood well about the contents of the study. If the patients personally consent to take part in the study, each of the investigator who gave the explanation, the study collaborator who provided a supplementary explanation, and the patient who received the explanations and consented should record the dates of the explanations or consent and sign the informed consent form approved by the IRB. The investigator should retain the signed informed consent form in the medical records and hand a copy of the signed informed consent form to the patient.

In the case where information, which may affect the patients' willingness to continue participating in the study, is obtained, the investigator should promptly notify it to the patients who are in the study, verify his or her willingness to continue his or her participation in the study, and record such a fact in a document. In addition, when the principal investigator judges that a revision of the written information to patients is necessary based on the information or because of other reasons, it should be promptly revised, and approval of the IRB should be obtained. After approval of the IRB, an explanation should be provided again using the revised written information to patients, and written informed consent should be obtained again.

13.2.3 Protection of Personal Information and Patient Identification

Personal information and information concerning privacy such as medical data should be recognized as those requiring strict protection and careful handling under the spirit of respecting individuals' personality, and full management measures should be taken to protect privacy. The Act on the Protection of Personal Information (Law No. 57 dated May 30, 2003; last revision, Law No. 49 dated June 5, 2009) should be followed.

13.3 Protection of Personal Information and Patient Identification

Personal information and information concerning privacy such as medical data should be recognized as those requiring strict protection and careful handling under the spirit of respecting individuals' personality, and full management measures should be taken to protect privacy. The Act on the Protection of Personal Information (Law No. 57 dated May 30, 2003; last revision, Law No. 49 dated June 5, 2009) should be followed.

13.3.1 Purposes of Using Personal Information, Items to Be Used and Methods of Use

1) Purposes of use

In this study, the patients' personal information will be used for the purpose of properly implementing monitoring, etc.

2) Items to be used

In consideration of the minimum necessity for identifying the patients and inquiries, items to be used will be as follows:

Enrollment No., patient identification (ID) No.

In other words, personal information other than the above items such as the patient's name will not be disclosed from the study sites to external parties. When study results are provided to parties other than the study sites, all information enabling to identify individuals will be anonymized and then provided.

3) Handling methods

The personal information and medical data of the patients should be collected through reporting to the data center by the investigator or study collaborators. In addition, personal information should not be exchanged by e-mail.

13.3.2 Secondary Use of Data

Data obtained from this study may be secondarily used (e.g., metaanalysis) in a manner that they are not link to information identifying individuals only if the coordinating committee and investigational drug suppliers approved.

13.3.3 Safety Management Responsibility System

When using personal information, safety management measures should be taken in accordance with rules at each study site to minimize the risk of information leakage. The data center should properly manage personal information in accordance with the guidelines for personal information handled by the National Cancer Center.

13.3.4 Handling of Disclosure of the Patients' Information

The person who handles a request for the disclosure of privacy information possessed by the study by the patients if any, will be in principle, the investigator at the study site where the patient is enrolled.

13.4 Approval of the Institutional Review Board (IRB)

13.4.1 Approval at the Start of the Study

When implementing this study, the principal investigator shall submit the protocol and documents specified by the GCP Ordinance such as the written information to patients to the head of the study site and receive approval of the IRB. As soon as approval of the IRB is granted, the principal investigator should send a copy of the written approval of the IRB and written information to patients (study site version) to the Clinical Study Coordinating Secretariat, and retain the original of the written approval of the IRB.

The contents of the protocol shall not be modified by the individual study sites. The protocol in common among all the study sites shall be used. When the IRB requested to modify the main text of the protocol, the principal investigator should discuss with the coordinating committee to consider its handling.

13.4.2 Approval of the IRB for the Appropriateness of Continuing the Study

The appropriateness of continuing the study shall be reviewed by the IRB once a year. If the IRB approved the continuation of the study, the principal investigator should send a copy of the written approval of the IRB to the Clinical Study Coordinating Secretariat, and retain the original of the written approval of the IRB.

13.4.3 Changes in the Contents of the Protcol

When revising the protocol, written information to patients and other relevant documents, it should be made in accordance with procedures for preparation of each document.

13.4.4 Categories of Changes in the Contents of the Protocol

In this study, changes in the contents of the protocol should be handles as amendments or revisions, and a supplementary explanation on the protocol should be handled as a memorandum or Q&A.

1) Amendment

An amendment refers to a partial change in the protocol that may increase risk to patients enrolled in the study or substantially affect the primary endpoint of the study. Approval of the efficacy and safety evaluation committee and each study site will be required.

2) Revision

A revision refers to a change in the protocol that may not increase risk to patients enrolled in the study nor substantially affect the primary endpoint of the study. Approval of each study site will be required. In addition, when the coordinating investigator determines that approval of the efficacy and safety evaluation committee is needed, a review should be requested.

3) Memorandum or Q&A

A memorandum or Q&A refers to not a change in the contents of the protocol but a supplementary explanation on the protocol to be distributed from the coordinating committee to study related persons for the purposes of reducing variances in interpretation of the document and particularly calling for attention. No review by or approval of the efficacy and safety evaluation committee is required.

